7.0 Multiple sites

This is a multi-site project funded by discretionary funding where the Principal Investigator is [name] located at the University of Michigan.

- A. University of Michigan School of Social Work is the coordinating site where all data will be entered, cleaned, stored, and analyzed.
- B. The Vocational Village located at Richard A. Handlon Correctional Facility, a level II, medium security prison in Ionia, Michigan is research site number 1. This vocational village can have up to 165 vocational trade students, 27 vocational trade tutors and 12 building trade workers. The villagers are housed together to promote a therapeutic, positive, and productive learning environment. At this site, we will recruit research participants to participate in this research study. Although data will be collected at this site, research staff will transfer the collected data in a locked box to the UM research site for processing.
- C. When new research sites become available the IRB will be notified and appropriate IRB documentation will submitted.

8.0 Risks to Participants:

This study involves villagers completing a battery of clinical, and role-play assessments.

There is minimal risk associated with participation in this study for villagers beyond potential boredom from navigating and using the computer program. All villagers will complete the studying within their vocational village setting. There are some sensitive questions that will be asked of participants (e.g. substance use), and possible emotional distress at some of the questions as well. Participants are allowed to skip over any questions they do not wish to answer.

Breach of confidentiality may be another potential risk. To mitigate this risk, participant files will only be referenced with a personal identification number (PINs). The document linking PINs to identifying information for participants will be password-protected and stored on a secure server protected by firewalls, or in REDCap, an encrypted and secure database website. Moreover, all videos of participant interviewing skills will be stored on a server that is password protected and secured behind firewalls.

There is a small risk that prison staff will attempt to access data. However, all effort will be made to prevent this. All surveys will only have PINs, so even if prison staff somehow sees completed surveys or forms, they will be unable to identify who completed them. Prison staff will not be expected to collect or view any of the survey information collected by study participants during the visits.

Confidentiality and safety procedures will be in full compliance with the University of Michigan policies. However, as with any research study, there is a risk of breach of confidentiality. The

prison staff will not be able to access the data provided by participants. If somehow they are able to access the data due to error, they will not be able to tell who the data belongs to as it will only be identified by a PIN.

When obtaining consent, participants are notified that they may stop participating at any time without repercussion. If consent is revoked in writing, the consent specifies the right to use or share information previously obtained as needed for the purpose of the study.

9.0 Potential Benefits to Participants:

Participants completing the intervention could possibly learn some new strategies to be more successful at Job Interviewing.

Results from this study may lead to a better understanding of helping improve job interview skills for justice involved individuals. It is therefore possible that results of this study may aid in intervention strategies for this population.

10.0 Provisions to Protect the Privacy Interests of Participants:

To minimize stress and fatigue during testing, participants will be assessed in an encouraging and accepting atmosphere. They can take breaks during the assessment process and may discontinue the assessment if they do not wish to continue. The research team have been trained in the administration of the research measures and have undergone training procedures to help minimize the stress this may cause.

The research assessments and intervention/SAU survey use will be conducted in a private or semi-private computer lab or educational room setting for the villagers. For teachers, the feedback form will be conducted in a setting of the participant's choosing. All methods of correspondence with teachers and leaders will be secure, including telephone, voicemails, text messages, or email. This correspondence will likely include scheduling times for research staff to visit the vocational village, timeline check-ins, as well as survey reminders. All participants will provide informed consent with respect to their preferred method of communication. In addition, we will use a personal identification number (PIN) to protect participant privacy by labeling all study documents with the PIN rather than any identifying information. The use of the PIN will help keep participant enrollment confidential. Teachers, leaders, and villagers will all be assigned this PIN.

Access to protected information will be limited to the PI and research team members. There will be a document located on the UM servers (password protected behind firewalls) that links PINs to study participant names. REDCap may also be used to link this information. The PI and research team will have access to this file in order to coordinate study visits and track participant progress to complete the study. REDCap, a HIPAA compliant and encrypted database may also be used to host protected participant information.

While testing participants at the villages, we will record data on either secure electronic equipment (local computing devices) or paper forms. This will be dependent on vocational village protocols. It is likely that all data will originally be on paper forms and then transferred to REDCap or secure UM server. If collected on a device, data will be uploaded to the server and removed from the device as soon as possible. All precautions will be taken to protect the electronic devices from theft or loss.

All forms and materials will be kept in a locked file in a locked room accessible only to research personnel at University of Michigan, not vocational village staff. Confidentiality procedures will be in full compliance with University of Michigan policies. Any confidential data obtained at the study site will be transferred back to the School of Social Work via a lock box to be secured into a locked file and in a locked room.

11.0 Confidentiality and Data Management:

Due to the funding from this project awarded by MICHR (from funds provided to MICHR by NIH), this research holds a Certificate of Confidentiality from the National Institutes of Health.

Description of Security measure to Protect Data Sources. Paper research records will be created and labeled with the PIN, where participants may provide consent and complete study measures. The document linking the subject PINs to identifiers will be maintained on a secure UM server at the School of Social Work. All study data will be stored in a locked cabinet within a locked office at the school. These records will serve as the source for electronic data entry. Research records will be transferred via a locked box to the UM research team where the data will be cleaned, re-entered into the electronic database, and the paper copies again stored in a locked drawer in a locked room. All records will be deidentified after study completion. No research data or records will be accessible to or shared with MDOC employees.

All participant documents at UM will be labeled with the participant's PIN. Each page of each document will be labeled with the PIN. Documents will be organized into a study binder that is also labeled with the participant PIN. All Binders and Study Documents will be stored in locked file drawers within a locked room.

Quality Assurance Measures. All participants will be recruited using strategies, documents, and text approved by the University of Michigan Institutional Review Board (IRB). The research team will regularly hold meetings to discuss the effectiveness of approved recruitment strategies and if new strategies should be reviewed by the IRB and then implemented. The PI will regularly audit accrual to ensure that participants meet eligibility criteria and that the study enrollment is consistent with the projected enrollment targets agreed upon with MICHR. In addition, the study coordinator will audit all study files to ensure that all required study data is completed on each form, and that there is no missing data. The REDCap system is accessible via a virtual private network that is password protected and

behind firewalls. The data will be transported from the schools to UM in a locked storage box. To protect confidentiality, all data will be numerically coded using a personal identification number (PIN), and information linking the PIN to the subject's name will be kept in a secured file cabinet and office and/or on REDCap. In addition, computer data files will be stored on password-protected computers and communication among the staff will use PINs, not names. No information concerning data will be presented with participant names. The biostatistician and project coordinator will also perform all necessary checks and controls to ensure the reliability and validity of the data, including monitoring data collection and collection procedures, data storage, data management, and data analysis.

12.0 Study Team Training for Data Collection within a Prison Setting

All study team staff members who will be working inside the vocational village prison settings will attend an information session with the PI, co-I's, lab manager, or study coordinator reviewing the protocol in detail, as well as the unique circumstances that may occur within the vocational villages. Staff will also review an additional training document and meeting as a method to support participant confidentiality. Additionally, study staff will also be trained to do the following:

If Any Deviation From Protocol Occurs:

If you are on site at one of the prisons and an incident occurs that deviates from out set protocol, please do the following:

- As soon as you are out of the facility, IMMEDIATELY call the Principal Investigator [name] and notify him of the situation. Follow given instructions accordingly.
 - a) If PI [name] is not available, call Co-Investigator [name].
 - b) If co-investigator [name] is not available, call Co-Investigator [name].
 - c) If co-investigator [name] is not available, call Team Manager [name].
 - d) If [name] is not available, call Study Coordinator [name].

If MDOC Staff Asks to Review Our Research Data:

Our research data is protected from MDOC review and should NOT be looked at by MDOC staff. However, if you are on site and MDOC staff asks if they can review video footage or tells you that you cannot leave the facilities without the data being reviewed, please do the following:

- Inform MDOC staff that we have a letter from [name], the MDOC Offender Success Administrator, stating that our research data is protected and is not to be reviewed by any staff at SMT or MTU.
- 2) Show MDOC staff printed letter from [name] and allow them to read it.
- 3) If MDOC staff is unsatisfied with the letter and/or still resisting, ask them to please call an in-house staff member who knows about our research and who can explain to them that our data is NOT to be reviewed and that this has been approved by the director.
 - a) If an in-house staff member is not available, ask them to call a Prison Supervisor.
 - b) If a Prison Supervisor is not available, ask them to call the Village Principal.

c) If the Village Principal is not available, ask them to call the Warden/Assistant Warden/Deputy Warden.

13.0 Data Analysis

H1: SAU+VR-JIT trainees will have higher employment rates than SAU-only by T3. To test H1, we will use multiple logistic regression and a Wald chi-square test of the coefficient to its standard error, to compare the adjusted employment proportions in the two conditions (attained a job = 1 vs. failed to attain a job or censored with a job = 0, between T1 and T3). Our MICHR-funded pilot trial does not have the resources to be an appropriately powered trial but instead we are using this pilot to estimate an effect size to use in a future adequately powered trial.

H2: SAU+VR-JIT trainees will have greater improvement in job-interview skills than SAU-only by T2. To test H2, we will conduct a repeated-measures analysis of variance (RM-ANOVA) with pretest and post-test interview scores as the repeated measures and treatment group as the fixed factor. Our MICHR-funded pilot trial does not have the resources to be an appropriately powered trial but instead we are using this pilot to estimate an effect size to use in a future adequately powered trial.

H3: SAU+VR-JIT trainees will have greater reductions in recidivism than SAU-only between T1 and T3. To test H3, we will compare recidivism percentages between SAU+VR-JIT and SAU-only at T3. Our MICHR-funded pilot trial does not have the resources to be an appropriately powered trial but instead we are using this pilot to estimate an effect size to use in a future adequately powered trial.

2.2.6 Analyses to Test Objective 2 are Based on Corbiere et al.'s [19] Model of Employment H5: Improved interviewing skills will mediate the relationship between VR-JIT (number of completed virtual interviews) and employment outcomes (i.e., obtaining employment). To test H5, we will test first for a significant SAU+VR-JIT impact on interview skills compared with SAU-only, then check for treatment by mediator interaction [81], then evaluate the product of the two coefficients [82] with bootstrapped confidence intervals [83].

Participants, Measures, Procedures, and Analyses.

A mixed-method process evaluation will entail conducting surveys and semi-structured interviews with villagers and teachers.

Surveys will be provided to N = 40 villagers randomized to VR-JIT to assess the acceptability and usability of VR-JIT. We will use items adapted from the Consolidated Framework for Implementation Research (CFIR) [43, 44]. Surveys adapted using CFIR will also be provided to the estimated N = 10 teachers from the Vocational Village (whom we will train to deliver VR-JIT) to assess provider views on VR-JIT acceptability, delivery strategies, and sustainability.

Exploratory Data

We will explore potential mechanisms for VR-JIT effectiveness (i.e., improved interview skills, attain a job), by first analyzing mediators (i.e., interview skills, self-confidence, and anxiety) and moderators using boot strapping (for mediators)⁴⁸ and linear regression (for moderators)⁴⁹. Second, we will explore potential mechanisms for a lack of improvement in interview skills and failure to attain a job) by examining group differences and associations between groups who did or did not have poor outcomes. Third, we will collect exploratory implementation data by interviewing vocational counselors and school administrators (N=10) about: 1) potential barriers and facilitators for VR-JIT implementation and scalability; and 2) how VR-JIT might reduce staff time required to deliver services. We will analyze this exploratory implementation data iteratively using thematic analysis and the constant comparative approach^{43, 44} to identify emergent themes regarding the barriers and facilitators of implementing VR-JIT.

14.0 Data Monitoring Plan to Ensure the Safety of Participants:

Data will be strictly monitored by the PI who regularly reviews testing and data management procedures to ensure protection of human subjects. We follow IRB and University of Michigan guidelines to minimize risk and report problems. We are required by our funding agency to report results annually. All data reported is de-identified prior to entry and analysis. We will initiate protocol revisions with the IRB when necessary. We have established a Data Safety and Monitoring Board to meet annually during the active recruitment phase of the study. The DSMB will review the research protocol and plans for data safety and monitoring, adverse events, risk management policies, and preliminary data analyssis. Members of the board include University of Michgan's [name], [name], Yale University's [name], and Department of Correction's [name].

All electronic data is stored on a secure server managed by University of Michigan School of Social Work, and access to the server requires a password and netID, and is fire walled, requiring VPN connection if off campus (per IT security protocols). An additional password is needed to access identifiable data stored on this secure server. Further, all data collected in the field is stored on encrypted drives and also identified only by ID number. All paper data is stored in locked filing cabinets in our lab at UM. Data analysis is completed by approved project personnel.

15.0 Qualifications to Conduct Research and Resources Available: Overview and anticipated contribution to success of the proposed work

The University of Michigan (UM) is one of the most resource intensive universities in the world, with state-of-the-art computing, statistical, library, and research consultation resources readily available to faculty researchers. The facilities and resources necessary for the proposed work are all currently available to [name] and his team. Below, the key units and facilities are described in detail to provide information about the specific contribution of each.

Office:

The facilities and resources necessary for the proposed work are all currently available to [name] and his team. [name] and the study staff have offices at the School of Social Work. The study staff and [name] have meeting and office space within the Curtis Research Center where [name] is the contributing faculty.

Computer:

The P.I. and the research staff have computer resources for data analysis and word processing for manuscript preparation.

Scientific Environment:

School of Social Work: The UM is a leader in social work education and research and is ranked first in the *U.S. News and World Report* rankings of social work programs. The interdisciplinary *Joint Doctoral Program in Social Work and Social Science* stands alone in the nation. This distinctive program trains academics, researchers, and practitioners to meet the challenges of society by utilizing theories and research from anthropology, economics, political science, psychology and sociology. There are approximately 600 MSW and approximately 75 Ph.D. students enrolled each term in the School of Social Work programs. For this project, [name] will regularly involve graduate students as work-study research assistants and they will facilitate data cleaning and double data entry in addition to other project supports.

The Vivian A. and James L. Curtis Research and Training Center: Through the generous contribution of the Curtis family, *The Vivian A. and James L. Curtis Research and Training Center* is funded to foster interdisciplinary externally funded research and UM-community evaluation research partnerships to advance knowledge in the areas of mental health, substance abuse, and health. The Curtis Center's research agenda focuses in studying health and mental health disparities and on the conduct of translational research to ameliorate these disparities. Center support includes study design consultation, advanced statistical consultation, grant and manuscript writing assistance, research space, and several other services. Expert consultation is provided by a multidisciplinary group of experienced, federally funded researchers. For this project, the Curtis Center will serve as the hub for the project staff and [name]. We will utilize its research consultation and research support resources to increase chances of success in completing the proposed project.

CTSA – (Clinical Translational Science Awards) and Michigan Institute for Clinical and Health Research (MICHR): The University of Michigan is the recipient of an NIH CTSA award, which has its home in MICHR (http://www.michr.umich.edu). MICHR provides a comprehensive institutional source of support and infrastructure for clinical and translational researchers at the University of Michigan. It is designed to serve any investigator, in any school of the University, performing clinical or translational research. It serves to connect and

integrate education, career development, infrastructure, and to catalyze research that spans the laboratory, the clinic, and the community. MICHR is organized in fourteen unique resource programs, focusing on the following domains: novel methods, technical core, Clinical Research Unit (MCRU), education/career development, biomedical informatics, regulatory support, pilot grants, biostatistics, research ethics, pediatric research, community engagement, clinical translation sciences, and health disparities research. Research Support Services include research development, data management and project management and monitoring (PMM) of federally funded, multi-center trials. MICHR offers all investigators expert consultation, budgeting and administrative support for project development, funding for pilot studies, the *Engage* participant recruitment portal, and support for clinical research management system, among other research development services. For this project, MICHR will provide assistance in data management, based on the REDCap platforms. REDCap is an electronic data capture (EDC) system that is secure, HIPAA compliant, and web-based. This easy-to-use, no-cost tool for the University of Michigan Clinical Researchers is intended to replace Microsoft Excel and Access. Using REDCap's stream-lined process for rapidly developing databases, an investigator may create, design, and manage clinical research data online. Further, REDCap provides automated export procedures for seamless data downloads to common statistical packages (SPSS, SAS, Stata, R), as well as a built-in scheduling calendar, ad hoc reporting tools, and advanced electronic data capture form features, such as branching logic, file uploading, and calculated fields.

Center for Statistical Consultation and Research (CSCAR): CSCAR is a service and research unit under the administrative oversight of the VPR that provides integrated, comprehensive statistical consulting services covering all aspects of research design and analysis from initial study design through presentation of research findings. CSCAR provides free statistical support to UM faculty and research staff and is located approximately three blocks from the School of Social Work. Among the CSCAR services provided are those related to proposal presentation and study design (e.g., power and sample size calculations), dataset consulting (e.g., database design, transferring datasets across platforms and different software packages), choice of statistical methods, use of statistical software (e.g., SAS, SPSS, SYSTAT, S-Plus, BMDP, JMP, LISREL, and AMOS on Windows, UNIX, and Macintosh platforms), interpretation of and presentation of results, collaborative research, workshops, remote consultation using "whiteboard" software, and geographic information systems consultation. With regard to computing resources, CSCAR provides PCs and Mac computers with the latest versions of a large number of software programs such as STATA, MPLUS, AMOS, MATLAB, R, SAS, SPSS, ArcGIS, and ArcView GIS, among others. The CSCAR Library PC also has a variety of statistical software packages available for use including a sample size and power analysis package. For this project, CSCAR will provide any statistical consultation needed to increase the chances of success of this project.

- 1. Carson, E.A., and D. Golinelli, *Prisoners in 2012: Trends in Admissions and Releases,* 1991–2012. 2013, Washington, DC: Office of Justice Programs, Bureau of Justice Statistics.
- 2. Alper, M., and M.R. Durose, 2018 Update on Prisoner Recidivism: A Nine-Year Follow-up Period (2005-2014). 2018, Washington, DC: Office of Justice Programs, Bureau of Justice Statistics.
- 3. Nally, J.M., et al., The Post-Release Employment and Recidivism among Different Types of Offenders with a Different Level of Education: A Five-Year Follow-up Study in Indiana. International Journal of Criminal Justice Sciences, 2014. **9**(1): 16–34.
- 4. Indianapolis-Marion County Commission, Indianapolis-Marion County City-County Council Re-Entry Police Study Commission Report, Indianapolis-Marion County City-County Council, Editor. 2013, Indianapolis-Marion County Council.

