- annually [1]. According to the 2018 Bureau of Justice Statistics, 44% of released prisoners were rearrested during the first year after release, 68% within three years, 79% within six years, and 83% within nine years [2]. These data suggest that more work is needed for the prison system to optimally provide rehabilitation and foster deterrence from future crime.
- 2.2 Employment Is an Important Protective Factor against Recidivism. Unemployment is often recognized as the leading mechanism of recidivism [3]. Moreover, unemployed offenders are approximately twice as likely to recidivate as employed offenders [4], though several other criminogenic risk factors contribute to recidivism (e.g., criminal history, antisocial behavior, poverty, age, race, and limited housing options) [5–7]. Among exoffenders who recidivate, employed ex-offenders stay in their communities for twice as long as unemployed ex-offenders [8]. Research suggests that employed ex-offenders are less likely to engage in predatory crime and use drugs and alcohol (which are known risk factors for recidivism) [9]. Gainful employment also enables ex-offenders to secure housing, pay their rent and utilities, and network within their communities [10, 11]. And maintaining employment reduces the incentive to commit crimes for monetary gain [12], which in turn helps reduce recidivism [10]. Unfortunately, ex-offenders have a difficult time obtaining employment after release [13], and only 25% of ex-offenders are employed within 12 months of reentry [14]. Therefore, finding ways to increase employment rates during reentry after prison is an urgent public-safety need.

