2.6 Closing the Job-Interview Training Gap in Vocational Services in General, and Especially in Prisons. The National Institute of Mental Health (NIMH) funded our team to develop and evaluate Virtual Interview Training (VR-JIT) for non-justice-involved individuals with mental illness in a series of lab-based efficacy RCTs (R44 MH080496). Briefly, VR-JIT is a computer-based job-interview simulation in which trainees repeatedly practice interviewing with a virtual hiring manager. Each interaction is facilitated with speech-recognition software and lasts approximately 25 minutes; there are 10 to 15 hours of unique virtual job interviews available. Our efficacy evaluation suggests that VR-JIT improved interview skills in five cohorts of adults with various disorders (depression, schizophrenia, PTSD, autism, addiction) [27–31] and increased their likelihood of getting job offers more than twofold within six months of completing VR-JIT [28, 31–33] (i.e., 14–25% of controls received job offers, compared with 48–54% of VR-JIT trainees).

Based on this work, our team received funding from the NIMH to evaluate the effectiveness, cost-effectiveness, and implementation of delivering VR-JIT to adults with severe mental illness receiving community-based vocational services (R01 MH110524), and funding from the Kessler Foundation to evaluate the effectiveness, cost-effectiveness, and implementation

of delivering VR-JIT to 1,000 high school students with disabilities receiving transition services. Our preliminary data in this recent work showed similar increases in interview skills and a twofold increase in job attainment by the eight-month follow-up [34, 35]. Thus, we have deep expertise at evaluating the effectiveness and implementation of VR-JIT. In addition, we received funding from the NIMH to adapt VR-JIT to meet the needs of transition-age youth (ages 16 to 26) with autism (R34 MH111531), and we are using internal funds to include additional modifications to support justice-involved individuals.

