There will be a few recruitment methods utilized to reach out to potential participants from the Vocational Village. First, inclusion and exclusion criteria will be shared with MDOC, Michican Department of Corrections Leaders and/or Teachers at the Vocational Village. MDOC Vocational Village staff will then identify a list of potential participants. We will then send Leaders and/or teachers a prepared flyer and/or letter to be distributed to those who might be eligible based off of the criteria. MDOC Vocational Village staff will use their own assessments in order to assess age, reading level, COMPAS Risk Assessment, possible impairments, etc. These assessments are for admittance to the Vocational Village as well as inclusion in this research study. After the flyer and/or letter is provided to villagers, study staff will schedule an information session with those identified villagers. The research team will inform villagers about the study during that time.

We will approach everyone who meets these eligibility requirements and will stress to the prison staff that we need to include and approach everyone equally without any "cherry-picking" by administration. We will also stress the voluntary nature of the study and the importance for all prison staff to be impartial. We believe that this method of recruitment will be the most fair in order to reach a wide potential of participants who will be able to utilize the virtual interview tool.

The MDOC administration estimates that we will be able to recruit approximately 60 villagers that meet inclusion criteria within a 12-month recruitment window. Using a 2:1 randomization model, we expect to enroll approximately 40 villagers in the SAU+VR-JIT group and 20 villagers in the SAU-only group. The Vocational Village will have no role in determining which arm participants are enrolled in; that process will be randomized and up to the University of Michigan staff.

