All participants will complete a follow-up survey, and the DSM-5 and SCL-10-R survey again. This should be approximately 15 minutes. Research staff will obtain contact information from MDOC so we can contact participants for their follow-up. The survey will be done via phone, email, or in-person depending on participant preference or their location. Participants will be compensated \$20 for each follow up survey that is completed. Also, the UM research team will request a bimonthly data pull from MDOC to obtain follow up data from participants if they cannot be reached by UM staff.

E. Participant Timelines

Villagers enrolled in the randomized controlled trial will complete all study visits within approximately 5 weeks of enrolling in the study Their participation will be complete after completing the 12-month follow-up

F. Vulnerable Population Safeguards

To reduce coercion or undue influence a private and safe place to consent villagers will be provided by The Michigan Department of Corrections (MDOC) at the Vocational Village. There will be no advantages or disadvantages provided to villagers for their participation. Villagers are notified that participation in this research will not have any influence on incarceration status to include in probation and parole decisions. With limited risks present in this research there is no requirement for a follow up examination after the completion of the study. MDOC will provide information on villagers reading level to inform the accessibility and understandability of all research material. It is expected that all villagers will be able to comprehend and understand the study. If we encounter a villager who may lack comprehension, we will not include them in the study.

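### The H1 outcome rule scores a participant censored after getting a job as 0, contradicting its own definition of success

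*Combined protocol and SAP*

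**What the plan says.** Section 13.0 (Data Analysis) tests H1 with a multiple logistic regression and a Wald test comparing adjusted employment proportions. The outcome is defined only in a parenthesis: "attained a job = 1 vs. failed to attain a job or censored with a job = 0, between T1 and T3". The same paragraph says the trial is not adequately powered and that "we are using this pilot to estimate an effect size to use in a future adequately powered trial".

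The employment outcome appears twice more in Section 13.0. H5 refers to "employment outcomes (i.e., obtaining employment", and the exploratory paragraph describes effectiveness as "improved interview skills, attain a job". Neither adds a censoring rule.

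Two provisions bear on how many people would be censored. Section 6.0, D.6 plans a periodic data request to the corrections department "to obtain follow up data from participants if they cannot be reached by UM staff", and amendment Ame00102494 adds postcards between follow-ups. Neither says how a censored participant is coded.

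**The concern.** The two codes are not mutually exclusive. Someone with a documented job between T1 and T3 who is then lost has attained a job (code 1) and has been censored while holding one (code 0). The more specific clause gives 0, so a literal reading records a known success as a failure. Two analysts following the plan could code the same person differently.

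The H1 estimate is meant to inform the design of a later trial. A literal application lowers the employment proportion in any arm where a job-holder is censored, and that error passes into the later trial's planning figure.

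**Working it through.** **The texts side by side.** In H1, H5 and the exploratory paragraph, getting a job is the favourable outcome. Only the censoring clause gives a job-holder the unfavourable code. No other section defines censoring, and none of the five listed amendments changes the rule. The contradiction therefore stands on the text alone; the arithmetic below only illustrates its possible size under the literal reading.

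**Inputs.**
- Arm sizes: Section 4.0 states "we expect to enroll approximately 40 villagers in the SAU+VR-JIT group and 20 villagers in the SAU-only group". This reproduces: 60 × 2/3 = 40 and 60 × 1/3 = 20. No power, alpha or dropout figure is stated for H1, so there is no design calculation to reproduce.
- Control rate p0 = 0.25. Section 2.2 states "only 25% of ex-offenders are employed within 12 months of reentry". It is also the top of the 14–25% control range in Section 2.6.
- VR-JIT rate p1 = 0.48, an assumption: the low end of the 48–54% in Section 2.6, which reports job offers in other populations ("of controls received job offers, compared with" VR-JIT trainees).
- Share c of job-holders who are censored: 10%, 20% and 30%, assumed because no figure is given.

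**Equal shares in both arms.** Coded rate = p × (1 − c). The odds ratio (OR) is then RR × [1 − p0(1 − c)] / [1 − p1(1 − c)], where the risk ratio RR = 0.48/0.25 = 1.92 for every c. With c = 0, OR = 1.92 × 0.75/0.52 = 2.77.

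| c | VR-JIT coded | Control coded | OR | Risk difference (points) |
|---|---|---|---|---|
| 0 | 0.480 | 0.250 | 2.77 | 23.0 |
| 10% | 0.432 | 0.225 | 2.62 | 20.7 |
| 20% | 0.384 | 0.200 | 2.49 | 18.4 |
| 30% | 0.336 | 0.175 | 2.39 | 16.1 |

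The expected number miscoded is (40 × 0.48 + 20 × 0.25) × c = 24.2c, or about 2, 5 and 7 of 60.

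**Unequal shares.** With 10% of control and 30% of VR-JIT job-holders censored, the coded rates are 0.225 and 0.336 and the OR is 1.74. With the shares reversed, they are 0.175 and 0.432 and the OR is 3.59. The documents do not suggest which direction is likelier.

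**In whole participants.** 48% of 40 is 19.2, taken as 19; 25% of 20 is 5.
- Correctly coded: (19/21)/(5/15) = 2.71. SE(log OR) = √(1/19 + 1/21 + 1/5 + 1/15) = 0.606, so the unadjusted Wald 95% CI is 0.83 to 8.90.
- Recoding 4 of 19 and 1 of 5 (about 20% each): (15/25)/(4/16) = 2.40, CI 0.67 to 8.54.
- Recoding only the 4 VR-JIT participants: (15/25)/(5/15) = 1.80.
- Recoding only the 1 control: (19/21)/(4/16) = 3.62.

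**Effect on a later trial.** Assume 1:1 allocation, two-sided alpha 0.05, 80% power and the usual pooled-variance formula for two proportions. Taking the coded proportions at face value gives 68 per arm at c = 0, and 80, 95 and 115 per arm at c = 10%, 20% and 30%.

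**The case against.** The strongest reply is that this is a slip. The surrounding text makes *without* the natural reading, an analyst counting jobs would hardly score a known job as 0, and under that reading the illustration above lapses. That is probably right about the intention. It does not remove the need for an edit, because the written rule is the only one. Under *without*, everyone lost with no recorded job counts as not employed; that is a substantive missing-data assumption and should be deliberate.

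The second reply is that few people may be affected. T3 is not defined. H2 ties T2 to the post-test, so T3 could be the six-month follow-up. It would then be the first planned survey after release, and someone who misses it would seldom have an earlier recorded job, apart from an early-released participant reporting one at a remote post-test (Ame00100925). If T3 is twelve months, a job at six months followed by loss is quite possible. The data request and postcards may also keep censoring low. All this stands as a limit on size, but it does not settle the code when the case arises.

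The third reply is that the figures rest on assumed censoring shares and on two rates that measure different things, and that the interval is unadjusted although the model is adjusted. That is correct. With equal shares the risk ratio does not move, and every whole-participant shift shown lies well inside the first interval.

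**Conclusion.** The concern holds. As written, the H1 outcome rule contradicts itself for anyone who gets a job and is then censored, and read literally it scores a documented success as a failure. Confidence in the contradiction is high; the effect on the result cannot be known from the documents. If equal shares of up to 30% of job-holders were censored, at assumed rates of 25% and 48%, the odds ratio would fall from 2.77 to as low as 2.39. Unequal shares could move it in either direction. This is small beside the sampling error of a 60-person pilot, but it is systematic and adds nothing useful to the estimate. It should be fixed before outcomes are analysed.

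**What to change.** Amend the H1 sentence in Section 13.0 so that any documented job attained between T1 and T3 is coded 1, regardless of later loss to follow-up. If *without* was the intended word, correct it and state plainly that participants lost with no recorded job are counted as not employed. It would help to say in the same place which follow-up T3 denotes and what counts as censored, since these determine how often the rule applies. The cost is one or two sentences of analysis text for the coding correction, with no new data and no extra analysis.
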